6.3. Assignment to Study Intervention

In this study, participants will be randomized 6:2 to phenserine or donepezil in an open-label manner. Drug Dispensing and Dosing Instructions

Randomized subjects will be dispensed a single bottle of phenserine or donepezil drug product on Day 0 following all baseline assessments and confirmation of eligibility. Each participant will take the first dose in clinic and be instructed on how to continue dosing at home through the next two weeks (5 mg bd for the phenserine group and 5 mg od for the donepezil group). As shown in Figure 1, at the end-of-Week 2 visit, participants will undergo safety and tolerability assessments, and will be tested to determine their cholinesterase inhibition level. Based on tolerability, participants in the phenserine treatment group may be titrated to the next higher dose level (10 mg bd) for the next two weeks of treatment, while participants in the donepezil arm will continue the 5 mg od regimen. Adequate supplies will continue to be provided to the participants at this visit and in future visits to ensure they have adequate study drug (with an appropriate overage) to ensure that there are no disruptions in their daily dosing regimen through to the next study visit. At the end-of-Week 4 visit, and based on safety/tolerability assessments, participants in the phenserine arm may be escalated to 10 mg tds through to the end-of-Week 8 visit and participants in the donepezil arm may escalate to 10 mg od and remain at that dose through the remainder of the study (i.e., end of Week 8, as long as it is tolerated. Participants in both arms will return for follow-up assessments at the end-of-Week 6.. At the end-of-Week 8 visit, all participants will undergo final on-drug study assessments and will then return to the site for a final safety follow-up visit within 1 week of the last study-drug dose.

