6.6. Dose Modification

As shown in the Study Schema (Figure 1), participants randomized to the phenserine arm will initiate dosing at 5 mg bd and maintain this dose for the first two weeks of study treatment. At the Week 3 visit, participants may be escalated to 10 mg bd, then 10mg tds (Figure 1), based on tolerability, including adverse events, clinical assessment, ECG and safety laboratory measurements. Participants who are unable to tolerate a higher dose will have their dose reduced to the next previous dose level and maintained at that dose through the remainder of the study. This clinical decision will be made by the study physician and the study team at each centre at the visit, or when any safety laboratory results are received during the days after the visit. If needed, the medical monitor and the PI will be contacted. All participants are expected to be at their individualized maintenance dose for 4 weeks (beginning of Week 5 through the end of Week 8).

Participants randomized to the donepezil arm, will initiate dosing at 5 mg od and will be evaluated at the Week 4 visit for dose escalation to 10 mg once daily. For participants in the phenserine arm, dosing will follow a stepwise escalation to ensure safety and efficacy:

- **Weeks 1-2:** Participants will begin with 5 mg twice daily (bd).
- **Weeks 3-4:** Participants will escalate to 10 mg twice daily (bd) if the initial dose is well tolerated.
- **Weeks 5-8:** Participants will further escalate to 10 mg three times daily (tds) based on continued tolerability.

Before any dose escalation, the dosage will be reassessed based on tolerability. If necessary, participants may be required to return to the center for a dose reduction. Throughout the study, dose adjustments will be made according to tolerability. Should any dose escalation lead to adverse effects that compromise the participant's well-being or safety, the dose will be reduced to the previously well-tolerated level. Participants will then continue at this adjusted dose for the remainder of the study period. These procedures are outlined in more detail in the dedicated SOP.

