11.7. Appendix 7: Subject diary

Sample of the subject diary for participants allocated to treatment with phenserine

Deltaker-ID: _____
Studiemedisin: fenserin

Navn på studielege: _____
Sykehus: _____
Telefon: _____

PATH-1 Studien
Behandlingsstudie for tidlig Alzheimer's sykdom
Behandling med fenserin

MEDISINDAGBOK

Deltaker-ID: _____

Formålet med denne medisindagboken er å hjelpe deg med daglig loggføring og oversikt over ditt inntak av studiemedisinen fenserin, som er en medisin under utprøving.

I tillegg kan du legge inn eventuelle bivirkninger eller andre hendelser som oppstår i løpet av behandlingsperioden. Vi vil også gjerne at du oppgir eventuelle endringer i den faste medisineringsplanen din hvis du tar andre medisiner i tillegg til fenserin.

Du vil få en instruksjon på hvordan du fører medisindagbok av studiepersonell på sykehuset.

I tillegg anbefaler vi deg følgende hjelpemidler:

- Dosett/pilleeske
- Sett inn en påminnelse på mobiltelefonen din
- Be din nærmeste pårørende om å minne deg på å ta medisinen din

I tekstboksen på neste side finner du doseringsplanen for behandling med fenserin, samt forholdsregler i tilfelle du glemmer en dose eller du tar for mye.

Deltaker-ID: _____
Studiemedisin: fenserin

Navn på studielege: _____
Sykehus: _____
Telefon: _____

Inntak av fenserin:

Kapselen skal svelges med et glass vann og bør tas sammen med mat. Kapselen skal ikke tygges eller knuses.

Doseopptreppingsplan for fenserin

1. Startdose
2 kapsler 5 mg daglig (1 kapsel morgen og kveld) i 2 uker
2. Dosering fra uke 3:
2 kapsler 10 mg daglig (1 kapsel morgen og kveld) i 2 uker
3. Dosering fra uke 5:
3 kapsler 10 mg daglig (1 kapsel morgen, ettermiddag og kveld) i 4 uker

Eller behandling etter avtale med din studielege

Dersom du har glemt å ta en kapsel

- Dersom du har glemt en dose og det er mindre enn 2 timer siden den skulle ha blitt tatt, kan du ta den glemte dosen.
- Hvis det har gått mer enn 2 timer siden den planlagte dosen, skal du vente til neste dose. Husk å kryss av for glemt dose i dagboken.

Tidsrom mellom dosene:

- 2 kapsler daglig: Ta dosene med et tidsrom på omtrent 12 timer (2 timer tidligere eller senere er akseptabelt).
- 3 kapsler daglig: Ta dosene med et tidsrom på omtrent 8 timer (2 timer tidligere eller senere er akseptabelt).

Dersom du tar for mye av fenserin

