DAG 26:	 5 mg  10 mg	 1 kapsel morgen  1 kapsel kveld	 1 kapsel morgen  1 kapsel kveld		
DAG 27:	 5 mg  10 mg	 1 kapsel morgen  1 kapsel kveld	 1 kapsel morgen  1 kapsel kveld		
DAG 28:	 5 mg  10 mg	 1 kapsel morgen  1 kapsel kveld	 1 kapsel morgen  1 kapsel kveld		
DAG 29:	 5 mg  10 mg	 1 kapsel morgen  1 kapsel kveld	 1 kapsel morgen  1 kapsel kveld		
DAG 30:	 5 mg  10 mg	 1 kapsel morgen  1 kapsel kveld	 1 kapsel morgen  1 kapsel kveld		
DAG 31:	 5 mg  10 mg	 1 kapsel morgen  1 kapsel kveld	 1 kapsel morgen  1 kapsel kveld		

PATH 1 studie
EU-CT: 2023-010262-00-00

side 5/10

v 1.1, 06.12.2024

Deftaker-ID: _____

Navn på studiefølge: _____

Studiemedisin: faseris

Sykehus: _____

Telefon: _____

Dag dato	Dose	Kryss av for antall kapsler du har tatt	Kryss av for glemt dose	Bivirkninger, symptomer	Endring i fast medisinplan
DAG 32:	 5 mg  10 mg	 1 kapsel morgen  1 kapsel ettermiddag  1 kapsel kveld	 1 kapsel morgen  1 kapsel ettermiddag  1 kapsel kveld		
DAG 33:	 5 mg  10 mg	 1 kapsel morgen  1 kapsel ettermiddag  1 kapsel kveld	 1 kapsel morgen  1 kapsel ettermiddag  1 kapsel kveld		

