3.4 Adherence and Protocol Deviations

3.4.1 Adherence to Allocated Treatment

Adherence to the allocated study treatment will be assessed for all participants who receive at least one dose of investigational medicinal product (IMP). Adherence is defined as the extent to which participants take the study medication according to the prescribed dosing regimen.

Compliance will be assessed using capsule counts and subject diaries and will be calculated as:

$$\% \text{ Compliance} = \left(\frac{\text{Number of capsules taken}}{\text{Number of capsules prescribed}} \right) \times 100$$

The number of capsules prescribed will be calculated based on the duration of treatment (date of last dose – date of first dose + 1) multiplied by the number of capsules prescribed per day according to the assigned dose level.

Compliance will be summarized by treatment group and overall. Participants will be classified as compliant if their calculated compliance is within 80–120% of the prescribed dosing, in accordance with the protocol definition.

The following summaries will be presented:

- Mean, median, and range of percentage compliance
- Number and percentage of participants classified as compliant
- Number and percentage of participants with compliance <80% or >120%

Compliance summaries will be descriptive only and no formal statistical comparisons will be performed.

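### The phenserine diary's daily log has no box for the afternoon capsule before Day 32, although its own instruction page starts three intakes a day at Week 5; the resulting undercount is small and confined to one arm

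*Protocol*

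**What the plan says.** **Schedule.** The instruction page of the phenserine diary (Protocol Appendix 7) sets two weeks at the start dose, then "2 kapsler 10 mg daglig (1 kapsel morgen og kveld) i 2 uker", then from Week 5 "3 kapsler 10 mg daglig (1 kapsel morgen, ettermiddag og kveld) i 4 uker". The protocol body agrees. Section 6.6 says of Weeks 5-8: "Participants will further escalate to 10 mg three times daily (tds) based on continued tolerability". Section 6.3 places the decision at the end-of-Week 4 visit, when "participants in the phenserine arm may be escalated to 10 mg tds through to the end-of-Week 8 visit". Tables 3 and 4 show the same weeks. The Schedule of Activities and SAP 2.4 put the Week 4 visit at Day 28 ± 3.

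**Day count.** Section 6.3 dispenses "drug product on Day 0 following all baseline assessments and confirmation of eligibility", with the first dose taken in clinic. The diary log also begins at Day 0.

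**Daily log.** Each row from Day 0 to Day 31 offers "1 kapsel morgen 1 kapsel kveld", once in the column for capsules taken and once in the column for forgotten doses. The third option, "1 kapsel ettermiddag", first appears on the Day 32 row.

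**Use of the diary.** Compliance is a secondary endpoint (Protocol Section 3 and Table 2). SAP 3.4.1 says: "Compliance will be assessed using capsule counts and subject diaries". It divides capsules taken by capsules prescribed over the whole treatment, at the daily number for the assigned dose level. Protocol Section 4.4 uses the returned-medication count to check the diary. Neither document says which source prevails when they differ.

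**The concern.** The diary contradicts itself at the step up to the highest regimen. For the days between escalation and Day 31, the instruction page prescribes an afternoon capsule that the log cannot record as taken or as missed, although Section 4.4.1 and the diary both ask participants to mark missed doses. The SAP denominator meanwhile charges three capsules for each of those days.

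Two things are at stake. Diary-based compliance is understated for a participant who did everything asked. And the check of diary against returned capsules shows a discrepancy that comes from the form and not from the participant.

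Both problems fall on one arm. The donepezil diary has one tablet box and a 5 mg/10 mg choice on every row, so it loses nothing at its own step up, and the SAP summarises compliance by arm.

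**Working it through.** **Inputs**
- Start dose for 2 weeks, next dose for 2 weeks (diary instruction page).
- First dose on Day 0 (Section 6.3).
- Week 4 visit on Day 25 to Day 31 (SAP 2.4).
- First row with an afternoon box: Day 32 (diary log).
- Two capsules a day before the step and three after it (Table 3, diary).
- Compliance limits 80-120% (Protocol Section 3, SAP 3.4.1).

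**Assumptions**
- The 56 treatment days are Days 0-55.
- The afternoon box continues on the later rows that are not shown; the sample ends at Day 40.
- The first three-capsule day is the day of the Week 4 visit or the day after. The documents do not say which.

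**Step 1: nominal start.** 14 + 14 = 28 days, Days 0-27, so Week 5 starts on Day 28. This matches the nominal Week 4 visit day.

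**Step 2: unrecordable capsules.** With *s* the first three-capsule day, the number is max(0, 32 − *s*).

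**Step 3: diary ceiling on the SAP definition.** Capsules prescribed = 2*s* + 3(56 − *s*). The most the log can hold is 2 × 32 + 3 × 24 = 136. The highest diary compliance for a fully adherent participant is 136 divided by capsules prescribed.

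| First three-capsule day | Unrecordable | Prescribed | Diary ceiling |
|---|---|---|---|
| 25 | 7 | 143 | 95.1% |
| 26 | 6 | 142 | 95.8% |
| 27 | 5 | 141 | 96.5% |
| 28 | 4 | 140 | 97.1% |
| 29 | 3 | 139 | 97.8% |
| 30 | 2 | 138 | 98.6% |
| 31 | 1 | 137 | 99.3% |
| 32 | 0 | 136 | 100% |

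If the new regimen starts the day after the visit, read one row lower: a Day 28 visit costs 3 capsules and a Day 31 visit costs none.

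**Step 4: a single visit interval.** Section 6.5 also assesses compliance at each visit, although the SAP plans no such output. For Days 28-41 the diary ceiling is (42 − 4)/42 = 90.5%. The worst case is a step on Day 25 with the Week 6 visit on Day 39: (42 − 7)/42 = 83.3%. Both stay above 80%. The slack does shrink. At least 34 of 42 capsules are needed for 80%, so a participant could normally miss 8. On diary data that falls to 38 − 34 = 4 or 35 − 34 = 1.

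**Step 5: could Week 6 exposure be affected?** The last affected day is Day 31 and the earliest Week 6 visit is Day 39. Days 32-38 lie between, which is 7 × 24 = 168 h. The protocol gives an elimination half-life of 6.53 h (Section 2.3.1) and 8.25 h for AChE inhibition (Section 4.5). 168/6.53 = 25.7 and 168/8.25 = 20.4 half-lives. Section 2.3.1 also reports no accumulation on repeated dosing.

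**The case against.** The case for leaving this alone has several parts.

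- *There is a second source.* Returned-capsule counts do not depend on the boxes. This stands, and it confines the error to the diary and to the cross-check.
- *Nothing hangs on the figure.* SAP 3.4.1 makes the compliance summaries descriptive, no analysis population in SAP Section 4 uses compliance, and it is not among the predefined major deviations in SAP 3.4.2. This stands too, and it keeps the point small.
- *The pages are only a sample.* The appendix says so. But they carry a version, a date and page numbers, and they show Days 22-40 row by row, so the label does not remove the mismatch. It leaves some doubt about the diary actually issued.
- *The layout changes just after the last permitted Week 4 visit day.* True, but that suits only the latest visits. At the nominal day, 3 or 4 capsules are still lost.

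A reader might also infer more than the documents support:

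- *The missing boxes cause missed doses.* This is conceivable in people with Alzheimer's disease, but no figure in the documents tests it. The diary's printed schedule and reminder tips, the dosing explanation at each visit (Section 4.4) and the study partner's role (Section 4.4.3) work against it.
- *Week 6 PK or AChE results would be distorted.* Even if afternoon capsules were skipped through Day 31, more than 20 half-lives would pass before the earliest Week 6 sample. A cumulative effect on exosome markers could be argued, but no figure supports one.
- *Every phenserine participant is affected.* Escalation depends on tolerability, and a Day 31 visit with the new regimen from Day 32 leaves no gap.

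**Conclusion.** The diary is wrong as printed: its daily log contradicts its own instruction page and Table 3. The effect is small. On the SAP's whole-treatment definition, a fully adherent participant's diary shows at most 97.1% if the step is on Day 28 and 95.1% if it is on Day 25, with 4 and 7 capsules unrecordable. The gap by itself moves nobody below 80%. On diary data alone it could matter only for someone already within about 3 to 5 percentage points of the limit (4/140 = 2.9%, 7/143 = 4.9%). The lasting harm is a one-arm undercount in a source for a stated secondary endpoint, together with false mismatches in the diary/count check and no rule for resolving them.

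These figures rest on Days 0-55 as the treatment days and on the sample pages matching the diary in use. They imply no view on the regimen or on when it should start.

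**What to change.** 1. **Diary.** Reconcile the daily log with the instruction page and Table 3. Print afternoon 'taken' and 'missed' boxes, with a 'not prescribed' option, on every row from Day 25, the earliest permitted Week 4 visit. Every visit day in the window then has zero unrecordable capsules. The cost is a reprint. The downside is unused boxes for participants who are not on three intakes. They must be told to mark 'not prescribed', so that an empty box is not read as a missed dose or as a prompt to take a capsule.

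2. **SAP 3.4.1.** Add one sentence: for phenserine participants who used the uncorrected diary, the returned-capsule count takes precedence over the diary for the whole visit intervals that contain the affected days. With escalation at the Week 4 visit, that is the Week 4 to Week 6 interval. The rule has to cover whole intervals because capsules are counted only at visits (Protocol Sections 9.4-9.7), so a count for Days 25-31 alone cannot be separated out. The cost is that dose-by-dose detail from the diary is not used for that interval.

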 **HELSE STAVANGER**
Stavanger University Hospital

SESAM
Regulert kompetensområde for informasjon og utveksling

Delaker-ID: _____ Navn på studielege: _____

Studiemedisin: doseprofil Sykehus: _____
Telefon: _____

Dag dato	Dose	Kryss av her om du har tatt din daglige dose	Kryss av her for glemt dose	Bivirkninger, symptomer	Endring i fast medisinplan
DAG 0: _____	 5 mg  10 mg	 1 tablett	 1 tablett		
DAG 1: _____	 5 mg  10 mg	 1 tablett	 1 tablett		
DAG 2: _____	 5 mg  10 mg	 1 tablett	 1 tablett		
DAG 3: _____	 5 mg  10 mg	 1 tablett	 1 tablett		
DAG 4: _____	 5 mg  10 mg	 1 tablett	 1 tablett		
DAG 5: _____	 5 mg  10 mg	 1 tablett	 1 tablett		
DAG 6: _____	 5 mg  10 mg	 1 tablett	 1 tablett		
DAG 7: _____	 5 mg  10 mg	 1 tablett	 1 tablett		
DAG 8: _____	 5 mg  10 mg	 1 tablett	 1 tablett		
DAG 9: _____	 5 mg  10 mg	 1 tablett	 1 tablett		
DAG 10: _____	 5 mg  10 mg	 1 tablett	 1 tablett		

Próbitt i studie
EU/CT: 2023-010283-00-00 side 2/8 v 1.1, 06.12.2024

 **HELSE STAVANGER**
Stavanger University Hospital

SESAM
Regulert kompetensområde for informasjon og utveksling

Delaker-ID: _____ Navn på studielege: _____

Studiemedisin: doseprofil Sykehus: _____
Telefon: _____

Dag dato	Dose	Kryss av her om du har tatt din daglige dose	Kryss av her for glemt dose	Bivirkninger, symptomer	Endring i fast medisinplan
DAG 11: _____	 5 mg  10 mg	 1 tablett	 1 tablett		
DAG 12: _____	 5 mg  10 mg	 1 tablett	 1 tablett		
DAG 13: _____	 5 mg  10 mg	 1 tablett	 1 tablett		
DAG 14: _____	 5 mg  10 mg	 1 tablett	 1 tablett		
DAG 15: _____	 5 mg  10 mg	 1 tablett	 1 tablett		
DAG 16: _____	 5 mg  10 mg	 1 tablett	 1 tablett		
DAG 17: _____	 5 mg  10 mg	 1 tablett	 1 tablett		
DAG 18: _____	 5 mg  10 mg	 1 tablett	 1 tablett		
DAG 19: _____	 5 mg  10 mg	 1 tablett	 1 tablett		
DAG 20: _____	 5 mg  10 mg	 1 tablett	 1 tablett		
DAG 21: _____	 5 mg  10 mg	 1 tablett	 1 tablett		

Próbitt i studie
EU/CT: 2023-010283-00-00 side 3/8 v 1.1, 06.12.2024

 **HELSE STAVANGER**
Stavanger University Hospital

SESAM
Regulert kompetensområde for informasjon og utveksling

Delaker-ID: _____ Navn på studielege: _____

Studiemedisin: doseprofil Sykehus: _____
Telefon: _____

Dag dato	Dose	Kryss av her om du har tatt din daglige dose	Kryss av her for glemt dose	Bivirkninger, symptomer	Endring i fast medisinplan
DAG 22: _____	 5 mg  10 mg	 1 tablett	 1 tablett		
DAG 23: _____	 5 mg  10 mg	 1 tablett	 1 tablett		
DAG 24: _____	 5 mg  10 mg	 1 tablett	 1 tablett		
DAG 25: _____	 5 mg  10 mg	 1 tablett	 1 tablett		
DAG 26: _____	 5 mg  10 mg	 1 tablett	 1 tablett		
DAG 27: _____	 5 mg  10 mg	 1 tablett	 1 tablett		
DAG 28: _____	 5 mg  10 mg	 1 tablett	 1 tablett		
DAG 29: _____	 5 mg  10 mg	 1 tablett	 1 tablett		
DAG 30: _____	 5 mg  10 mg	 1 tablett	 1 tablett		
DAG 31: _____	 5 mg  10 mg	 1 tablett	 1 tablett		
DAG 32: _____	 5 mg  10 mg	 1 tablett	 1 tablett		

Próbitt i studie
EU/CT: 2023-010283-00-00 side 4/8 v 1.1, 06.12.2024

 **HELSE STAVANGER**
Stavanger University Hospital

SESAM
Regulert kompetensområde for informasjon og utveksling

Delaker-ID: _____ Navn på studielege: _____

Studiemedisin: doseprofil Sykehus: _____
Telefon: _____

Dag dato	Dose	Kryss av her om du har tatt din daglige dose	Kryss av her for glemt dose	Bivirkninger, symptomer	Endring i fast medisinplan
DAG 33: _____	 5 mg  10 mg	 1 tablett	 1 tablett		
DAG 34: _____	 5 mg  10 mg	 1 tablett	 1 tablett		
DAG 35: _____	 5 mg  10 mg	 1 tablett	 1 tablett		
DAG 36: _____	 5 mg  10 mg	 1 tablett	 1 tablett		
DAG 37: _____	 5 mg  10 mg	 1 tablett	 1 tablett		
DAG 38: _____	 5 mg  10 mg	 1 tablett	 1 tablett		
DAG 39: _____	 5 mg  10 mg	 1 tablett	 1 tablett		
DAG 40: _____	 5 mg  10 mg	 1 tablett	 1 tablett		
DAG 41: _____	 5 mg  10 mg	 1 tablett	 1 tablett		
DAG 42: _____	 5 mg  10 mg	 1 tablett	 1 tablett		
DAG 43: _____	 5 mg  10 mg	 1 tablett	 1 tablett		

Próbitt i studie
EU/CT: 2023-010283-00-00 side 5/8 v 1.1, 06.12.2024

11.8. Appendix 8: Procedure and prescription template for dispensing donepezil

Procedure for dispensing donepezil to study subjects in PATH-1 study:

- The study investigator at the coordinating site Stavanger University Hospital will submit an e-prescription on white prescription for treatment with donepezil for 4 participants (prescription per participant: 1x28 pack of 5 mg and 1x 50 pack of 10 mg).
- When a participant is randomized to treatment with donepezil at one of the hospitals, the study nurse will obtain a letter of authorization from the participant to be able to collect the prescription (which is in the participant's name) at the local hospital pharmacy.
- The prescription template (see text box below) will be handed out with the medicine package for donepezil. Dosing is carried out in accordance with the package insert.
- The contents of the medicine package (28 pieces for 5 mg and 50 pieces for 10 mg) will be recorded on a drug accountability log before it is dispensed to the participant. Due to frequent study visits (every 2 weeks), the participant will only receive one pack of medicine at a time.
- For each study visit, the participant is encouraged to bring the entire medication package, including empty blisters, for counting, record and compliance check. Dose titration of donepezil according to the package leaflet and instruction on the subject diary from week 5. The participant will return leftovers from 5 mg tablets, as well as the medicine package and receive a new pack of 10 mg. Delivery and return will be recorded on the drug accountability log.
- Leftover medicine is destroyed in accordance with local hospital routines.
- In addition, various tests and examinations will be taken during the study visits. Should there be side effects or contraindications with the treatment, the study investigator will re-evaluate the treatment dose (as in normal clinical practice).

Text template for dispensing a prescription for donepezil in the PATH-1 study:

TIL KLINISK UTPRØVNING

EU-CT nummer: 2023-510282-10-00

Studienavn: PATH-1

Utpøver: [name]

Adresse: SESAM, [name],
[name]

Telefonnummer: [name]

Deltaker-ID: _____

BRUKSANVISNING:

1 tablett 5 mg daglig i 4 uker, deretter 1 tablett 10 mg i 6 uker, eller
etter avtale med studielege.

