
Sykehus: _____

Telefon: _____

PATH-1 Studien

Behandlingsstudie for tidlig Alzheimer's sykdom

Behandling med donepezil

MEDISINDAGBOK

Deltaker-ID: _____

Formålet med denne medisindagboken er å hjelpe deg med daglig loggføring og oversikt over ditt inntak av medisinen donepezil, som er en godkjent medisin mot mild og moderat grad av Alzheimers sykdom.

I tillegg kan du legge inn eventuelle bivirkninger eller andre hendelser som oppstår i løpet av behandlingsperioden. Vi vil også gjerne at du oppgir eventuelle endringer i den faste medisineringsplanen din hvis du tar andre medisiner i tillegg til donepezil.

Du vil få en instruksjon på hvordan du fører medisindagbok av studiepersonell på sykehuset.

Inntak av donepezil:

Kan tas med eller uten mat. Knusing/deling anbefales ikke.

Dosering

1. Startdose
5 mg en gang daglig. Donepezil tas oralt om kvelden, like før sengetid.
2. Dosering fra uke 5:
10 mg en gang daglig. Donepezil tas oralt om kvelden, like før sengetid.

Eller behandling etter avtale med din studielege.

Dersom du glemmer å ta en tablett, tar du en tablett neste dag til vanlig tid. Du skal ikke ta dobbel dose som erstatning for en glemt dose.

Dersom du tar for mye av donepezil, ber vi deg ta kontakt med din studielege (telefonnr.: _____), fastlege eller sykehus så raskt som mulig.

Se pakningsvedlegg for mer informasjon om bivirkninger og kontraindikasjoner for donepezil.

This is just a sample of the first 4 pages of the diary. The diary will cover the entire treatment period.

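### The single 28-tablet pack of 5 mg donepezil does not cover a Week 4 visit as late as Day 31, which is in window, despite the overage promised in section 6.3

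*Protocol*

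**What the plan says.** Protocol Appendix 8 (11.8) sets the donepezil supply: "prescription per participant: 1x28 pack of 5 mg and 1x 50 pack of 10 mg". It adds that "the participant will only receive one pack of medicine at a time", and describes the change of strength as an exchange: "The participant will return leftovers from 5 mg tablets, as well as the medicine package and receive a new pack of 10 mg". The label text gives the first stage as "1 tablett 5 mg daglig i 4 uker" (one 5 mg tablet daily for four weeks).

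Protocol 6.3 starts the clock on Day 0: "Randomized subjects will be dispensed a single bottle of phenserine or donepezil drug product on Day 0" and "Each participant will take the first dose in clinic". The donepezil diary in Appendix 7 (11.7) has a Day 0 row and sets dosing in the evening: "5 mg en gang daglig. Donepezil tas oralt om kvelden, like før sengetid". Sections 6.3 and 6.6 place the escalation decision at the Week 4 visit. Protocol Table 1 and SAP 2.4 both allow that visit at Day 28 ± 3 days.

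On supply in general, section 6.3 says that participants will hold enough study drug, "with an appropriate overage) to ensure that there are no disruptions in their daily dosing regimen through to the next study visit". Table 1 also marks study drug dispensing at Week 2.

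**The concern.** The 5 mg pack is sized for exactly four weeks, while the visit at which it is replaced may fall three days later than that. A participant who follows every instruction and attends late but in window would run out before the visit. Appendix 8 provides no second 5 mg pack, so the overage promised in section 6.3 is not delivered at this stage.

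Week 4 is a scheduled exosome, AChE and ECG visit, and it is one level of the Visit factor in the SAP 7.2 model. SAP 2.4 admits in-window assessments to the analysis, so samples taken after such a gap would be used like any others. Protocol 2.1 includes donepezil specifically to control for cholinesterase inhibition, and the arm has 4 participants. An unplanned break in dosing just before AChE and exosome sampling therefore bears on what the comparator is there to do.

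**Working it through.** **Inputs**
- 5 mg tablets supplied: 28 (Appendix 8).
- Dose: 1 tablet daily, in the evening (Appendix 7).
- First dose: Day 0 (6.3).
- Week 4 visit on day d, with d from 25 to 31 (Table 1, SAP 2.4).

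**The plan's own figure.** 4 weeks × 7 days × 1 tablet = 28. The pack size is right for exactly four weeks. Overage against the nominal stage: 28 − 28 = 0 tablets.

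**Shortfall before the visit.** With evening dosing, the visit-day dose comes from the new pack. Doses due from Day 0 to the day before the visit number d.
- A, Day 0 tablet from the pack: max(0, d − 28).
- B, Day 0 tablet from elsewhere: max(0, d − 1 − 28).
- C, as A, but the visit-day dose is due before the visit: max(0, d + 1 − 28).

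| Visit day | A | B | C |
|---|---|---|---|
| 25 to 27 | 0 | 0 | 0 |
| 28 | 0 | 0 | 1 |
| 29 | 1 | 0 | 2 |
| 30 | 2 | 1 | 3 |
| 31 | 3 | 2 | 4 |

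A follows the diary and section 6.3 most directly. Each dose missed earlier leaves a spare tablet and shortens the gap by one day; each lost tablet lengthens it by one.

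**Quantity needed.** A visit on Day 31 needs tablets for Days 0 to 30, which is 31 under A (32 under C). The pack is 3 short (4 under C), before any overage.

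**Second stage.** The 10 mg pack holds 50. The longest in-window stage is Day 25 to Day 59: 59 − 25 + 1 = 35 days, leaving 50 − 35 = 15. On the label's six weeks, 50 − 42 = 8 remain. This stage is not short.

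**Would the compliance check show it?** SAP 3.4.1 divides doses taken by the days from first to last dose. With three doses missed over Days 0 to 56, this is 54/57 = 94.7%, inside 80–120%. Protocol 6.5 also assesses compliance at each visit. If Week 2 falls on Day 17 and Week 4 on Day 31, 17 tablets have gone by Week 2 and 28 − 17 = 11 remain for the 14 doses due on Days 17 to 30: 11/14 = 78.6%, below 80%.

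**The case against.** The strongest reply is that the main text already covers this. Table 1 marks dispensing at Week 2, section 6.3 requires adequate supplies at that visit, one pack at a time does not forbid a further pack then, and donepezil is a commercial product held at local pharmacies. The label also allows dosing as agreed with the study physician. What stands is that an alert site could avoid the gap. But Appendix 8 is the operative supply procedure; it prescribes one 5 mg pack per participant and describes no top-up. The Week 2 mark and the label wording supply no tablets.

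It is also fair that the gap is conditional. It needs a visit on Day 29 to 31 and nearly full adherence beforehand. Three of the seven in-window days are affected under A, but that is a count of days and not a probability; the target, Day 28, gives no gap with evening dosing.

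Four stronger readings may tempt a reader, and the documents do not support them:
- *The gap puts the arms on an unequal footing because phenserine participants have an overage.* The promise in 6.3 covers both arms, and no phenserine capsule count is given.
- *The gap can never breach the compliance limit.* That holds for the SAP whole-treatment measure, but the per-visit count above can fall below 80%.
- *The primary result is biased.* SAP 4.5 gives the primary timeframe as baseline to Week 8; Week 4 is intermediate, and the second-stage supply is ample.
- *The AChE target endpoint is damaged.* The protocol defines that endpoint for the phenserine arm only.

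**Conclusion.** The point holds as an inconsistency between the prescribed quantity, the visit window and the supply promise in section 6.3. A fully adherent participant on evening dosing, whose Day 0 tablet came from the pack, misses 1, 2 or 3 doses before an in-window visit on Day 29, 30 or 31. The figures are 0, 1 or 2 if the Day 0 tablet came from elsewhere, and 2, 3 or 4 (with 1 for a Day 28 visit) if the visit-day dose is due before the visit.

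One affected participant is 1 of 4, or 25%, of the comparator arm at Week 4. That describes exposure to the problem; it is not an estimate of bias. Neither document says how far a gap of this length would move AChE activity, the exosome markers or the ECG. The consequence is limited to Week 4 samples and to a change of strength that follows an unplanned interruption. This is worth correcting because it is easy to correct, but it does not threaten the trial's main comparison.

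**What to change.** Reconcile Appendix 8 with section 6.3 and the Week 4 window. The prescribed first-stage quantity should cover every in-window visit day, which means at least 31 tablets for Days 0 to 30 with evening dosing, plus an overage stated as a number. State also whether the Day 0 clinic dose comes from the participant's pack, and bring the one-pack-at-a-time wording into line with the quantity chosen. Leftovers would be returned at Week 4, as Appendix 8 already requires.

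No change to the dose or the visit schedule is proposed. In particular, a tighter visit limit for donepezil alone would make Week 4 timing differ between the arms.

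The cost is a small additional pack for 4 participants and an edit to one appendix.
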